5.1 INCLUSION CRITERIA

- (1) 18 years of age and older.
- (2) diagnosed with a brain CA (single or multiple).
- (3) had a SH within the past year (with demonstrated new lesional bleeding or hemorrhagic growth >3mm on diagnostic studies AND attributable new symptoms).
- (4) ~~no prior treatment of the symptomatic lesion (after neurosurgical consultation)~~. Subject is able to provide informed consent.

5.2 EXCLUSION CRITERIA

- (1) have symptomatic spinal CA's
- (2) have received prior brain irradiation.
- (3) cases where verification of SH with clinical and imaging review cannot be accomplished.
- (4) No prior or planned treatment of the symptomatic lesion (after neurosurgical consultation)

Subjects meeting these eligibility criteria are considered eligible for the SCA arm.

Additional FUBV Arm Exclusion Criteria. To be eligible for Aims 2 and 3, CASH cases enrolled in Aim 1 will be further excluded from FUBV arm inclusion for the following reasons:

- (1) unable to undergo MRI with contrast and/or because of contraindications (e.g. pacemaker, metallic foreign body, pregnancy) or other reasons (severe claustrophobia, too large or too heavy for MRI scanner).
- (2) pregnant or breastfeeding women due to unknown harm to fetus/child from MRI.
- (3) Subject will be unable/unlikely to return for follow-up visit

5.4 SCREEN FAILURES

Sites will enter all patients with CCM disease seen at their institution. The study database (VISION-EDC) will include a list of possible exclusions from which the study team will choose for all patients found to be not eligible for the trial. The most common reason for exclusion is likely to be a lack of symptomatic hemorrhage within the last year.

This a non-interventional study.

7 STUDY INTERVENTION DISCONTINUATION AND PARTICIPANT DISCONTINUATION/WITHDRAWAL

7.1 PARTICIPANT DISCONTINUATION/WITHDRAWAL FROM THE STUDY

Cases whose CASH lesion has been resected will be considered to have reached endpoint, and will not be followed further during the study. The indication for surgery shall be noted, including any SH prior to CASH lesion resection.

Cases who develop a recurrent SH during follow-up, and their CASH lesion has not been excised, will remain in the study until they complete follow-up. They will undergo the scheduled follow-up assessments at Years 1 and 2.

Participants are free to withdraw from participation in the study at any time upon request.

7.2 LOST TO FOLLOW-UP

If an enrolled subject decides to discontinue the study, fails follow-up, or develops an exclusion criterion after enrollment in the study (becomes pregnant, undergoes CASH lesion excision, etc.), he/she will be considered an attrition after recording the causative event. Data collected prior to the attrition shall still be included in the study. An allowance in sample size calculation is made for up to 30% attrition or missing data from any cause.

The following actions must be taken if a participant fails to return to the clinic for a required study visit:

- The site will attempt to contact the participant and reschedule the missed visit [within 2 months of the study window] and counsel the participant on the importance of maintaining the assigned visit schedule and ascertain if the participant wishes to and/or should continue in the study.
- Before a participant is deemed lost to follow-up, the investigator or designee will make every effort to regain contact with the participant (where possible, 3 telephone calls and, if necessary, a certified letter to the participant's last known mailing address or local equivalent methods). These contact attempts should be documented in the participant's medical record or study file.
- Should the participant continue to be unreachable, he or she will be considered to have withdrawn from the study with a primary reason of lost to follow-up.

8 STUDY ASSESSMENTS AND PROCEDURES

All eligible subjects will be identified by the study team at each site. Based on clinic schedules and current patient databases, all CCM patients with a symptomatic hemorrhage within the last 12 months (of screening) are eligible for the trial. Sites will screen neurology, neurosurgery, and neurointerventional radiology clinic schedules, MRI schedules, and attend Neurovascular rounds to help identify potential subjects. Additionally, study sites will rely on referrals from the various services listed above, or self-referrals via web searches and through the Angioma Alliance, a patient support group. Once identified, the study coordinator at each site, along with the site PI, will screen the subject for basic eligibility. Screened subjects not scheduled to come in for a clinical visit within their eligibility window will be contacted by the study coordinator or PI to explain the study and determine if the subject is interested. When the subject comes in, either for a standard clinic visit or for a study visit, the study team will review the subject's medical history to ensure the subject meets the inclusion criteria. The trial will be explained and informed consent obtained. After consent is obtained a physical exam (height, weight, vital signs) will be completed, a baseline modified Rankin Score obtained, and EQ-5D, PROMIS 29, and NIH stroke scale assessments completed. The study team will also collect information about the subject's history, pertinent to the disease (history of seizure, resection of other lesions, etc.). All subjects at the FUBV sites (enrolled to the FUBV arm) will have a MRI scan including the additional sequences for research as specified in Specific Aim 2 (QSM/DCEQP). All women of childbearing age will undergo a urine or serum beta-HCG pregnancy test prior to MRI to confirm no pregnancy, per local institutional guidelines.

Subjects enrolled in the FUBV arm will return for 2 follow up visits: one at 12 months and the other at 24 months. Excluding the informed consent process, all baseline procedures will be repeated. Subjects will have completed their participation upon completion of the baseline visit procedures (SCA arm) or the year 2 visit (FUBV arm). All subjects enrolled in the SCA arm will have one study visit only.

FUBV subjects will receive travel stipends for each of the 3 study visits. Those subjects traveling less than 200 miles to the enrolling site will receive \$50 per visit (baseline, Year 1, Year 2). Those traveling more than 200 miles to the enrolling site will receive \$500 per visit (baseline, Year 1, Year 2).

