4.1 OVERALL DESIGN

This is an observational cohort study of CASH cases with no intervention. Seven high-volume cavernous angioma sites have been identified for this project. We propose to activate sites and prepare data structure in year 1, then prospectively screen and enroll 200 CASH cases in years 2-5 at multiple sites. We shall collect harmonized baseline data, and enroll a subset of approximately 120 cases into the follow-up and imaging biomarker validation (FUBV) arm at 4 or so sites to assess and compare clinical outcomes, biomarker outcomes, and functional status and patient-reported quality of life outcomes for potential use in future clinical trials.

Clinical Coordinating Center (CCC):

The Clinical Coordinating Center, located at the University of Chicago, will train site coordinators on the protocol and data entry, as well as track enrollment rates. The CCC will also be responsible for answering site questions about enrollment and subject eligibility.

Data Coordinating Center (DCC):

The Data Coordinating Center, located at Johns Hopkins University, will develop and oversee the trial electronic data system to ensure the integrity of data collection, safety and coordination of data storage and access. Study site staff will be trained, sites activated and pilot cases completed in year 1 and data collection thereafter for years 2-5. The DCC shall perform data monitoring and generate data reports for analysis by Investigators as proposed in the respective Specific Aims 1-3. The DCC will review the online case forms for completeness, logic, and consistency, then verify the entered data against the uploaded source records/data collection worksheets in a random 5% sample of cases. Routine queries identified in this process will be entered into the EDC system (triggering an automated notice to the site). The monitors will then work with the site personnel to obtain correction of all data errors and resolution of the corresponding queries.

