9.2 SAMPLE SIZE DETERMINATION

Screening and Clinical Assessment (SCA) Arm: We calculated the width of the exact 95% CI for detecting CASH cases, varying the prevalence from 10% to 25% based on the range in preliminary data, and total sample sizes screened from 500 to 1,500. Based on these sample size models, we propose recruiting 200 CASH cases for the SCA arm of this project, to be enrolled during years 2-5, an average of 50 cases/year at all sites, and less than one case/site/month. Assuming a 15% prevalence of CASH cases (the average in three ongoing registries), a screening sample size of 1,333 would be required over a 4-year period (333 cases to be screened/year) to detect 200 CASH cases \pm 2% (i.e., 13% to 17%). Even if the true prevalence is lower (e.g. 10%) or higher (25%), we will have excellent precision to within \pm 1.5% to 2.5%, respectively, corresponding to 134 - 334 CASH cases for the same screening sample size. These CASH sample sizes will also allow flexibility in describing the proportion of important subgroups (i.e. sex, lesion location, genotype), and provide realistic estimates of recruitment at SCA sites (screened/enrolled ratio).

The 7 main sites are all high-volume CA clinical centers, with demonstrated ability to screen the requisite number of cases. Their recent clinical activity is demonstrated by the number of CA cases (n) seen over a 12-month period with diagnosis ICD9 228.02 on initial or follow-up visits at each of the institutions: 1) University of Chicago (n=106), 2) Mayo Clinic-Rochester (n=70), 3) University of New Mexico (n=80), 4) University of Utah (n=40), and 5) Barrow Neurological Institute, Phoenix (n=200); TOTAL (n=496). We would need to screen 1,333 CA cases over a 4-year period at the 5 sites (333 CAs screened each year), in order to identify and enroll 200 CASH cases, based on the estimated prevalence of 15% CASH cases among overall CA cases. This is a very realistic target, with 496 CAs actually evaluated per year at the 5 sites for the SCA arm. To help meet the target enrollment, The University of California- San

Francisco (n=70) was added as a recruitment site in February 2019 and Johns Hopkins University (n=150) will be added in 2020. If we do not meet our target enrollment of CASH cases, we may add additional, yet to be decided on, sites.

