9.3 POPULATIONS FOR ANALYSES

Cavernous angiomas with symptomatic hemorrhage (CASH) are most likely to re-bleed and cause further neurologic sequelae. It would be desirable to develop a drug that stabilizes CASH, and prevent recurrent bleeding. CASH with recent bleed, where surgical resection is not undertaken, are the most likely cases to be followed expectantly per current evidence based guidelines, with clinical equipoise for testing novel therapies to prevent re-bleeding. They are the most likely cases to be targeted for clinical trials.

Appropriate and complete statistical modeling of data collected by the sites for both SCA/FUBV arms are imperative to the planning, development, and completion of a successful Phase III interventional trial. The most critical component is the accurate assessment of the enrollment rates of CASH across several sites, as well as the between-site variability in these estimates. Both within and between sites variability will be used to adequately power a Phase III trial, will be calculated by developing random-effect models along with using appropriate link functions quantifying the rates of CASH in these models.

As a follow-up step, in-depth data analyses will be performed using the demographic, imaging, clinical and biomarker data collected. These are applied to develop models assessing how predictive each of these factors is to the development of recurrent SH. Understanding which factors are most predictive of SH will be crucial in developing a covariate adaptive randomization scheme for the Phase III trial that insures proper balance in these prognostic factors between treatment arms. Finally, statistical assessments of changes in lesional iron content and permeability biomarkers, QOL, mRS, and NIHSS during follow-up of CASH patients will be performed. Understanding how these measures change over time will be an important step in the process of developing hypotheses on the effect of treatment on these as putative secondary or surrogate outcomes, or as potential composite outcomes.

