10.1.2 STUDY DISCONTINUATION AND CLOSURE

The study may be modified or discontinued at any time by the IRB, the NINDS, the PI, the OHRP, or other government agencies as part of their duties to ensure that research subjects are protected. Additionally, yearly go/no-go decision points have been built into the study, as described below.

Timeline/Milestones		Go/ No-Go Decision Points
Year 1	
IRB approval for sites, DCC and CoresSite activation, training and regulatory compliance certification of personnel.Finalize electronic data forms, data entry protocols for SCA and FUBV sites.Screen at least 10 cases and enroll 1 CASH case at each SCA/FUBV site.Feasibility and phantom validations of QSM and DCEQP measurements at FUBV sites.	
Activate alternate sites as needed (per site activation milestones).Reject QSM or DCEQP if they fail validation test thresholds at FUBV sites (adjust budget if imaging biomarkers are rejected).
Year 2	
Screen at least 50 cases and enroll of 10 CASH cases at each SCA/FUBV site, with successful completion of initial clinical, functional status and imaging assessments.Quality certification of clinical data acquisition, and validation of biomarker assessments by the BIC on enrolled cases.	
Activate alternate sites as needed (per site performance or recruitment rates).Optimize baseline and outcomes collection instruments per problems with each.Reject QSM or DCEQP if they fail ongoing quality assurance threshold at interim midterm review (adjust project budget)Change follow-up to 6 & 18 months. (instead of 12 & 24) per timing/rate of recurrent SH at midterm review.

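### The enrollment-rate analysis and the yearly site milestones do not separate a possible opening pool of known cases from steady-state accrual

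*Combined protocol and SAP*

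**What the plan says.** - **Case-finding (section 8).** Identification draws on clinic schedules and databases: "Based on clinic schedules and current patient databases, all CCM patients with a symptomatic hemorrhage within the last 12 months (of screening) are eligible". Clinic and MRI schedules, rounds, referrals and self-referrals are also listed. Known patients are approached actively: "Screened subjects not scheduled to come in for a clinical visit within their eligibility window will be contacted by the study coordinator or PI".
- **Eligibility (5.1).** The patient must have "had a SH within the past year". Nothing requires the SH to follow site activation.
- **Target (4.1, 9.2).** The study will "prospectively screen and enroll 200 CASH cases in years 2-5", which 9.2 puts at "an average of 50 cases/year at all sites, and less than one case/site/month".
- **Use of the rate (9.3).** "The most critical component is the accurate assessment of the enrollment rates of CASH across several sites, as well as the between-site variability". It is to be estimated with random-effect models. No term for time since site opening is mentioned, nor any split by SH date. The synopsis lists enrollment rates in its first primary objective.
- **Milestones (10.1.2).** One enrolled case per site in Year 1, 10 per site in Year 2 (with at least 50 screened), and 10 per site per year in Years 3-4. The Year 2 action is "Activate alternate sites as needed (per site performance or recruitment rates)".
- **Staggered opening (9.2).** One site "was added as a recruitment site in February 2019 and Johns Hopkins University (n=150) will be added in 2020".
- **Data held (9.4.1).** Time from SH is among the minimum variables collected.

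**The concern.** Accrual can come from two sources that behave differently. One is a stock: patients already known to the site at opening whose SH fell in the preceding 12 months and who remain eligible. It can be used once. The other is a flow: new SHs after opening, which continue for as long as the site recruits. An average over all enrollments mixes the two in a proportion that depends on how long the site was open.

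Section 4.2 says these rates are needed to decide how many sites a future trial requires. A mixed average carries over only to a trial with the same look-back and the same recruitment length per site. The Year 2 milestone is the most exposed figure, because a site's first full recruiting year is when any pool is enrolled.

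**Working it through.** **1. The plan's own figures (9.2).** 200/0.15 = 1,333 screened; 1,333/4 = 333 a year; 200/4 = 50 enrolled a year. These reproduce, and the exact 95% CI for 200/1,333 is 13.1% to 17.0%, in line with the stated 13% to 17%.

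**2. Model.** Let I be a site's steady number of eligible enrollments per year, T its recruiting time in years, and f the share of one year's cases waiting at opening, over and above ordinary flow. Then:

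- expected enrollments = I × (T + f)
- average rate = I × (1 + f/T)
- relative excess over the steady rate = f/T

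The documents do not give f. The value 1 is a ceiling: prior or planned treatment, refusal and non-contact all lower it, and if patients usually enroll L months after the SH, f is at most 1 − L/12.

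| f | Excess, first year | Excess, 4 years | Steady rate if 200 enroll in 4 years, 200/(4 + f) |
|---|---|---|---|
| 0.25 | 25% | 6.3% | 47.1 a year |
| 0.5 | 50% | 12.5% | 44.4 a year |
| 0.75 | 75% | 18.8% | 42.1 a year |
| 1 | 100% | 25% | 40.0 a year |

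The last column assumes that all sites recruit for the full 4 years.

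**3. Year 2 milestone of 10.** The milestone's minimum of 50 screened, at the plan's 15%, gives 50 × 0.15 = 7.5 steady cases. This is close to the planned average over seven sites, 50/7 = 7.1. With a Poisson count of mean 7.5 × (1 + f), assuming the whole pool is enrolled in that year:

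- f = 0: P(10 or more) = 0.22
- f = 0.25: 0.46
- f = 0.5: 0.69
- f = 1: 0.93

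The steady rate at which 10 is the expected count is 10/(1 + f): 8.0, 6.7 and 5.0 a year for f = 0.25, 0.5 and 1.

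This matters for sites near the threshold. Taking 15% of the annual volumes in 9.2 gives 6.0 a year at the smallest site (40 × 0.15) and 10.5 to 30 at the other six, before refusals and exclusions.

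**4. Transfer to a later trial.** If that trial uses the same look-back and recruits for R years per site, its average is I × (1 + f/R). With f = 1 and R = 2 this is 1.5 × I, against 1.25 × I here over 4 years. This study would then understate yield (1.25/1.5 = 0.83). For R above 4 it would overstate it. For a trial with no opening pool the overstatement is the 6-25% above.

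**5. Between-site comparison.** Two sites with equal flow, open for 2 and 4 years, would show a ratio of apparent rates of 1.25/1.125 = 1.11 (f = 0.5) or 1.5/1.25 = 1.20 (f = 1). For the spread across sites, take true rates as 15% of the seven volumes in 9.2:

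- No pool: coefficient of variation (CV) 0.540.
- Equal f and T everywhere: CV unchanged; only the absolute SD rises with the mean (×1.25 at f = 1, T = 4).
- f = 1 with assumed durations of 4 years for five sites and 3 and 2.5 years for the two late ones: CV 0.547.
- Pool at the four smaller sites only: CV 0.44. At the three larger only: CV 0.64.

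The direction is not fixed.

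**The case against.** Several objections have force.

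- **The opening sweep is inferred.** A reader might take section 8 to say that each site begins by working through its database for a year of past cases. It does not. It describes continuing identification through several channels, with databases as one, and 4.1 calls screening prospective. The text permits a pool; it neither prescribes one nor gives its size.
- **The bias is not one-way.** A reader might infer that Phase III would be planned with too few sites. Section 4.2 names SH within the prior year and an unresected lesion as the likely trial eligibility, so a later trial could open with its own pool. Step 4 shows that the error can go either way.
- **Between-site variability is not inflated by design.** Step 5 shows no change in relative spread with equal pools and durations, and movement either way otherwise. The documents give no opening dates for the first five sites, so actual durations cannot be derived.
- **Other Aim 1 estimates are untouched.** The proportion of CASH among all CA cases (9.1, 9.4.1) is not a rate per unit time, and f/T does not apply to it. It would be affected only if database-found CASH cases entered the numerator without the other database patients entering the denominator. Section 9.3 also leaves open what its model counts per unit time.
- **The milestones partly correct themselves.** The target of 10 recurs in Years 3-4, enrollment is tracked centrally, and sites have been added. Pool cases are valid cases towards 200. Some of the pool may be used in Year 1, though that milestone asks for only one case per site.

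What remains is that the quantity to be estimated (start-up plus steady accrual, or steady accrual alone) is undefined. Correction through the later milestones also comes late: an alternate follow-up site opened in Years 3-4 of a 5-year study has little room for 24 months of follow-up.

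**Conclusion.** The point holds as a gap in defining the enrollment rate, and it is a cheap improvement rather than a flaw that invalidates the study. If a pool exists, a simple average rate exceeds the steady rate by 6-25% over 4 years and 25-100% in a site's first year. A site at 7.5 steady cases a year would meet the Year 2 milestone with probability 0.46-0.93 instead of 0.22. These figures rest on f between 0.25 and 1, which is an assumption, on constant incidence, and on a rate counted per site and unit time. The consequence for Phase III depends on recruitment length per site. Site comparisons may be confounded by opening date, but the documents do not support a claim that variability is overstated.

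**What to change.** In 9.3 and 9.4.1:

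1. Classify each enrolled case by whether the qualifying SH fell before, or on or after, site activation, using the time from SH already collected and the activation date.
2. Fit the site random-effect rate model to post-activation SH cases per active site-month, and state this as the steady-state rate.
3. Report the opening pool as a separate count per site.
4. Project Phase III accrual as steady rate × duration plus one opening pool per site, where that trial's look-back allows a pool.
5. Tabulate enrollment by time since activation. With a 12-month window, no pre-activation SH still qualifies from month 13, so accrual from then on is a check on step 2. Step 2 can run slightly low, because ordinary delay between SH and enrollment places some normal-flow cases in the pool.

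In 10.1.2, show both counts when the Year 2 milestone is reviewed. Judging sites on post-activation cases alone would be a preference, not a necessity.

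The cost is analysis wording, with no new data collection. The steady rate rests on fewer cases, T/(T + f): 4/5 = 80% of enrollments over 4 years at f = 1 and 4/4.25 = 94% at f = 0.25. It will also look less favourable than the pooled average.

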Knowledge Gaps Regarding the Prevalence of CASH and Baseline Characteristics. For planning and executing multi-site clinical trials, it is unclear what fraction of CA patients would meet the likely trial eligibility criteria of SH within the prior year with an unresected lesion. That prevalence varied between 10-25% in the three largest ongoing CA research databases at U.S. institutions, with different referral patterns and enrollment criteria. This might vary further at other institutions, and with systematic screening. **Prospective prevalence of CASH in systematic screening of CAs, and enrollment rates at multiple sites are not known.** These data are essential for the proper design of clinical trials, including the number of prospective sites needed. It is further unclear how CASH cases might vary by age, sex, familial versus sporadic, lesion size and location, associated venous anomaly, past bleeds, and baseline disability. These features varied or were not assessed consistently in the 3 active prospective CA research databases in the U.S. More importantly, the **assessment of these features at multiple sites has never been harmonized or adjudicated. Further, it is unclear what functional status and Quality of Life (QoL) instruments best capture the clinical impact of CASH.** Inclusion/exclusion criteria and stratification for these characteristics will be important in clinical trials, as they will impact natural risk, and potentially the effect of putative therapies. These critical knowledge gaps will be addressed in Specific Aim 1 of this proposal.

Opportunities and Challenges with Novel Biomarkers Linked to Clinical Bleeding in CAs.

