9.1 STATISTICAL HYPOTHESES AND PROPOSED ANALYSES

Specific Aim 1. Descriptive statistics (frequencies, min, max, mean, standard deviation) and contingency table analysis will be performed to identify any possible coding errors. Data inconsistencies identified will be sent back to sites for correction. We will calculate the proportion and exact 95% confidence interval (CI) of CASH cases among all CA cases at each SCA site and overall. Baseline characteristics will be summarized using chi-square tests for categorical variables and t-tests for continuous variables. EQ-5D measures are scored on the T-score metric, with a mean of 50 and standard deviation (SD) of 10 in a referent population (mild, moderate, and severe impairment is defined as 0.5-1.0 SD, 1.0-2.0 SD, or 2.0+ worse than the mean, respectively). Spearman correlation coefficients will be calculated between mRS and Euro-QoL and PROMIS29 scales, and mean scores of Euro-QoL and PROMIS29 will be stratified by mRS levels. This analysis will allow us to determine ceiling effects of scores and how well the Euro-QoL and PROMIS29 data are distributed in CASH cases. Functional and QOL scores shall also be analyzed by pre-defined subgroups (sex, genotype and lesion location), to inform stratification or the need for adaptive randomization in clinical trials.

Specific Aim 2. This will follow the same design for QSM and DCEQP data acquired using these phantoms. A $p<0.05$ will be considered a failure, or significant non-zero difference. The accuracy of QSM and DCEQP values will be assessed at each of the sites participating in the FUBV arm by estimating the coefficient of determination r^2 between the observed and known phantom values, with $r^2 \geq 0.95$ needed to validate accuracy of each technique³⁵. The Pearson's correlation coefficients r of the FUBV subjects will also be compared using Fisher transformation. The precision of QSM and DCEQP measurements will be tested by comparing two separate measurements acquired at each site, using a paired t-test (7 ferumoxytol concentrations acquired twice by QSM, and 7 permeability values simulated with the phantom twice by DCEQP). The reproducibility of phantom measurements will be evaluated by comparing the QSM and DCEQP simulation values acquired at New Mexico and Mayo Rochester against the values obtained at Chicago, and one another, using a two-sample t-test.

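### Self-referred patients are pooled with schedule-screened patients in the CASH proportion, and route of entry is not among the listed data items, so probable enrichment cannot be separated from prevalence under systematic screening

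*Combined protocol and SAP*

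**What the plan says.** Section 4.2 states the gap that Aim 1 is to fill: "Prospective prevalence of CASH in systematic screening of CAs, and enrollment rates at multiple sites are not known". Prevalence under systematic screening and the enrollment rate are named as two quantities.

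Section 8 lists how patients are found. Clinic schedules, MRI schedules and neurovascular rounds come first, then referrals from those same services, and then "self-referrals via web searches and through the Angioma Alliance, a patient support group". All of them pass through the same eligibility check, and a patient may attend for a study visit rather than a routine clinic visit.

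Section 5.4 sets the denominator: "Sites will enter all patients with CCM disease seen at their institution". Sections 9.1 and 9.4.1 give the estimator: "We will calculate the proportion and exact 95% confidence interval (CI) of CASH cases among all CA cases at each SCA site and overall".

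The items kept for screen failures (section 2.3) are age, gender, race, sporadic or familial disease, and reason for exclusion. Section 9.4.1 gives a minimum variable list and leaves the final list to Year 1. Neither includes route of entry. I found no section that excludes self-referrals from the proportion, analyzes them separately, or plans a sensitivity analysis by route.

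**The concern.** A patient found on a clinic list is in the pool whether or not the lesion has bled recently. A patient who contacts a site about this study may be there because it has. Section 5.1 admits only patients with a symptomatic hemorrhage in the preceding year, so people who seek the study out are likely to include more CASH cases than the clinic list does. Each such patient adds one to both numerator and denominator.

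The pooled figure then answers a different question from the one in section 4.2. The plan wants a realistic screened-to-enrolled ratio (section 9.2), intends to use within- and between-site variability to power a Phase III trial (section 9.3), and makes the number of subjects and sites a formal decision (section 10.1.2). If self-referral is concentrated at some sites, between-site differences would partly reflect how patients arrived. Without a route field, the analyst could not undo this afterwards.

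**Working it through.** **Inputs from the documents (section 9.2).** The assumed CASH prevalence is 15%, the mean of three registries. The number to screen is derived from it: "a screening sample size of 1,333 would be required over a 4-year period". The target behind that number is 200 cases: "we propose recruiting 200 CASH cases for the SCA arm of this project". The interval is the exact two-sided 95% CI, examined for prevalences from 10% to 25%.

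**Reproducing the plan's figure.** 200 / 0.15 = 1,333.3, which agrees with 1,333. The exact (Clopper-Pearson) 95% CI for 200/1,333 is 13.1% to 17.0%, which agrees with 13% to 17%. At 10% the half-width is 1.6 points (stated 1.5), and at 25% it is 2.4 points (stated 2.5). The arithmetic is sound, but these intervals cover sampling error only.

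**Inputs not in the documents (assumed).** Let f be the self-referred share of the screened pool and q the CASH fraction among self-referrals. Neither is given. I take f from 2% to 10%, and q as 50% or 100%.

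**Effect on the proportion.** With p the CASH proportion among systematically identified patients,

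observed proportion = (1 − f) × p + f × q, so bias = f × (q − p).

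The bias is zero if q = p and upward for any q above p. With p = 15%:

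| f | q = 50% | q = 100% |
|---|---|---|
| 2% | 15.7% | 16.7% |
| 5% | 16.8% | 19.3% |
| 10% | 18.5% | 23.5% |

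**Share that produces a 2-point shift.** Set f × (q − 0.15) = 0.02.

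- q = 100%: f = 0.02 / 0.85 = 2.4%, or about 31 of 1,333. Check: (1,302 × 0.15 + 31) / 1,333 = 226.3 / 1,333 = 17.0%.
- q = 50%: f = 0.02 / 0.35 = 5.7%, or about 76 of 1,333.

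**The same question within the planned totals.** Suppose s of the 200 CASH cases are self-referred and all self-referrals have CASH. The systematic proportion is (200 − s) / (1,333 − s).

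- s = 10: 190/1,323 = 14.4% (exact CI 12.5% to 16.4%)
- s = 20: 180/1,313 = 13.7% (11.9% to 15.7%)
- s = 40: 160/1,293 = 12.4% (10.6% to 14.3%)

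At s = 20, a site network relying on systematic screening alone would need 200 × 1,313 / 180 = 1,459 screened for 200 cases, against 1,333 planned, or 9% more.

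**By site.** Small sites are more sensitive. Section 9.2 gives Utah 40 CA cases in 12 months, so 160 over four years and 24 CASH at 15%. Ten additional CASH self-referrals (assumed) would give 34/170 = 20.0%.

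**The case against.** The strongest reply is that Aim 1 is formally about enrollment rates (section 3), and section 9.3 calls these the most critical component. For that quantity a self-referred patient is genuine yield, and a future trial may well recruit through the same patient group. This stands. It is why self-referrals should be kept and reported, and why the point is confined to the prevalence estimate that section 4.2 names alongside enrollment.

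Second, nothing says that self-referrals have CASH. Someone with any cavernous angioma may get in touch, be logged as a screen failure, and enter the denominator only. This also stands as a limit: enrichment is an inference from the eligibility rule. A reader might infer that the bias is upward with certainty, but the documents do not establish q. Section 5.4 ties entry to being seen at the institution and does not say whether someone turned away before a visit is logged, so q could lie well below or close to 100%.

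Third, a reader might treat all referrals in section 8 as study-driven. The text does not support that: service referrals come from the clinics whose schedules are already screened, and largely overlap them.

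Fourth, a reader might conclude that the result would leave the stated 13% to 17%. Adding 50 CASH self-referrals to the planned totals does give 250/1,383 = 18.1%, but that presumes 250 cases against a target of 200 and that every added patient has CASH. Moreover, 13% to 17% is the interval expected at an assumed 15%, not an acceptance range; the plan itself allows for 10% to 25%.

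Reporting by site, and the random-effect models of section 9.3, describe differences between sites. They do not remove enrichment within a site.

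**Conclusion.** The concern holds in a limited form. The plan sets out to learn prevalence under systematic screening but estimates it from a pool that includes self-referrals, without listing the field needed to tell the groups apart. Self-referrals are probably enriched for CASH; if so, the proportion is too high overall and by site, and its exact CI does not reflect this.

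The size is unknown. It rests on two quantities that the documents do not give: the self-referred share and the CASH fraction among self-referrals. Under the assumptions shown, a share between about 2.4% (all CASH) and 5.7% (half CASH) would equal the stated 2-point precision. If self-referral is rare, or self-referrals resemble the clinic population, the effect is negligible; only recording the route can show which applies.

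A reader might go further and infer that future trials will be planned with too few sites. That would follow only if those trials recruit without web or patient-group referral, and the documents do not say so.

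**What to change.** Record route of entry for every screened patient, including screen failures, with a precedence rule: a patient whose first contact with the site was self-referral for this study counts as self-referred even if later found on a clinic schedule, and service referrals from the screened clinics count as systematic. Section 9.4.1 describes its variable list as a minimum, so the field fits the plan's own process.

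In sections 9.1 and 9.4.1, estimate the CASH proportion and its exact 95% CI, by site and overall, in systematically identified patients. Report the all-source proportion and yield alongside it as the recruitment measure. Presenting both matters because some self-referred patients might have been seen at these centers anyway, so excluding them could slightly understate prevalence.

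The cost is one extra field, one extra table and a slightly smaller denominator. Precision is hardly affected: for 180/1,313 the half-width is (15.7 − 11.9) / 2 = 1.9 points, against (17.0 − 13.1) / 2, or about 2.0 points, for 200/1,333.
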